Examining the Active Ingredients of Consultation to Improve Implementation of a Parent-mediated Intervention for Children With Autism in the Community Mental Health System

NCT04654117

06/17/2024

This study will examine which components of consultation are most helpful in improving clinical services that community providers deliver to Medicaid-enrolled children with autism spectrum disorder (ASD). Specifically, the project will focus on parent-mediated intervention, which is a best practice for improving skills in children with autism spectrum disorder. Previous work from our research team demonstrated very low frequency of billing claims for parent-mediated intervention within the Medicaid Autism Benefit – nearly half of children had not received a parent-mediated intervention session over the course of 6 months, and only 2.7% received parent-mediated intervention at a frequency that is consistent with evidence-based models (Straiton et al., 2021a). Qualitative data illustrated that providers are also largely unaware of evidence-based components of parent-mediated intervention sessions (e.g., care-giver practice with feedback). Our work highlighted that providers in this system are underprepared to deliver parent-mediated interventions and perceive numerous barriers at the family-, provider-, and agency-levels (Straiton et al., 2021b), such as perceived limited engagement and interest from caregivers, limited provider training, and competing demands on providers' time. This research demonstrated that providers desired training in the delivery of a manualized parent-mediated intervention that could be delivered via telehealth during the pandemic to address social communication deficits in children with ASD (Project ImPACT). The current project will address this need by supporting providers in this same system to use a manualized parent-mediated intervention with their clients with ASD. We will also be able to examine which components of consultation are most helpful in supporting providers to use this best practice within this system.

Specific Aim 1: Identify the potential active ingredients of the consultation model by evaluating its effects on providers' treatment adherence and parent-mediated intervention competence. I

predict that the feedback component will improve adherence and competence over and above improvements from the case support and skill rehearsal components.

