Specific Aim 2: Examine the relative feasibility, acceptability, and appropriateness of each consultation component using a single-case design: component analysis. Feasibility is the extent to which a practice can be successfully carried out within a setting. Acceptability is the extent to which a practice is agreeable and satisfactory. Appropriateness is the perceived fit or relevance of a practice to address a problem. I predict that providers will perceive the case support component to be the most feasible, acceptable, and appropriate of all components.

Specific Aim 3: Examine the effects of the consultation model on case penetration and the feasibility, acceptability, and appropriateness of the intervention (Project ImPACT). I predict case penetration (i.e., total number of Project ImPACT cases on a provider's caseload divided by the total number of eligible clients) and intervention feasibility, acceptability, and appropriateness to increase over time.

Exploratory Aim 4: Demonstrate associated social communication outcomes for Medicaid-enrolled children with ASD from baseline to post-consultation. Given that consultation leads to improved adherence and child outcomes and Project ImPACT results in improved child social communication outcomes, I predict that our consultation model will be associated with improvements in child social communication skills.

Experimental Design and Procedure

This study sought to examine the active ingredients of group consultation using a component analysis design, which is a type of single-case experimental design that allows for causal interpretation of the effects of treatment elements within a treatment package. This study was approved by Michigan State University's Institutional Review Board. Methodology is largely consistent with published standards for single-case design (Kratochwill et al., 2013). In this study, we capitalized on the use of advanced statistics (i.e., multilevel modeling) to quantify the effects of consultation components on clinician fidelity within our ABCD component analysis with multiple baselines. Descriptions of the study design are provided below.

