Design overview. Groups of 3-5 clinicians were recruited by each agency leader. Once all clinicians at an agency were enrolled, they had a 2-week initial training period in which they completed the Project ImPACT Beginner e-Course, a 6-hour self-directed online tutorial on Project ImPACT intervention content. The Beginner e-Course consisted of didactic modules with slides and audio recordings about Project ImPACT NDBI intervention strategies and best practices for collaborating with parents. Modules included video examples of caregivers implementing the intervention strategies and periodic quizzes about course content, but did not include explicit instruction about parent coaching.

Following the initial training period, clinicians entered the Baseline Phase (3 to 9 weeks; randomized by agency) during which they were asked to follow the Project ImPACT coaching manual and meet weekly with their enrolled families, but did not receive consultation support. After the baseline phase, all enrolled clinicians at each agency entered the consultation phase, during which they received 12 group consultation sessions, once per week, for 1.5 hours per session. The consultation phase included three, 4-week blocks in which the group completed one consultation training activity per block (i.e., case support, skill rehearsal, or feedback on

videotaped sessions). Clinicians submitted recordings of all Project ImPACT telehealth sessions throughout the Baseline and Consultation phases, and then again at Follow Up (8-weeks post consultation). Information about the procedures used in each phase is outlined below.

Baseline phase. Clinicians received an e-book copy of the Project ImPACT Coaching Manual, which includes detailed descriptions about the theoretical underpinnings of the intervention and lesson plans for each of the 24 sessions (e.g., session agendas, handouts, access to video models of NDBI intervention strategies, examples of trouble-shooting tips for common challenges with clients). Clinicians also received an e-book copy of the Project ImPACT Parent Manual, which includes descriptions of the NDBI strategies in parent-friendly language and tips about how to apply NDBI strategies at home and in the community. Clinicians were instructed to follow the lesson plans in the Project ImPACT coach manual and no consultation support was provided during the Baseline phase.

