Baseline lengths were randomized by a statistician unaware of agency characteristics using a random-number generator. Published standards for single-case designs require a minimum of 3 observations per phase to “meet standards with reservations” (Kratochwill et al., 2013). See Table 2 for the baseline lengths for each agency. Baseline lengths for agencies 1-4 were randomized for 3-6 weeks. Due to a methodological challenge (outlined below), baseline lengths for agencies #5 and #6 were randomized for 6-9 weeks to ensure that clinicians had sufficient baselines.

Consultation phase. Group consultation sessions took place via a teleconference platform (Zoom). During a given consultation condition (i.e., 4-week block in which only one consultation training activity was delivered), no components of any other conditions were provided. For example, during the skill rehearsal condition, no feedback was given about the role

plays, so that the only performance feedback clinicians received occurred in the feedback condition. All providers received each of the 3 consultation conditions (i.e., training activities), with each training activity delivered in isolation for a given 4-week consultation period. The order in which providers received each component was randomized for each agency by a statistician unaware of agency characteristics using a random-number generator, such that each agency had an equal chance of receiving one of the predetermined permutations of conditions (e.g., equally as likely to be randomized to ABCD order as ADCB order). Consultation sessions were rescheduled for the following week if more than half of participants at an agency would not be present or if the consultant would not be present. See Table 2 for the consultation component order for each agency.

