Case support condition. With one week's notice, clinicians were asked to brainstorm at least one implementation challenge that they experienced recently when delivering Project ImPACT (e.g., getting the caregiver to complete live practice during sessions, uncertainty about how to complete Practice Plan worksheets). At the beginning of each case support consultation session, the consultant screenshared a blank note-taking table and asked each clinician to list recent challenges they've had when implementing Project ImPACT. She asked all other clinicians to endorse whether they also experienced that challenge. Once all challenges were listed, she asked the group to choose 2-3 challenges to problem-solve during the present session. The consultant then asked the group of clinicians to brainstorm possible solutions for each selected challenge, noting their responses and any specific resources/handouts that were mentioned. Once the clinicians finished listing possible solutions, the consultant added her own ideas of possible solutions. Topics included challenges with telehealth, confusion about intervention content and/or handouts, and addressing client/family needs (e.g., difficulty

promoting caregiver engagement in session). Problem-solving specifically addressed ways to improve implementation of Project ImPACT within that particular agency's setting (e.g., within the resource constraints of that agency). Once the group agreed that they had no additional ideas for possible solutions, the consultant moved on to the next selected implementation challenge. Any challenges that remained were kept in the note-taking table to be discussed at the next case support session, if clinicians desired. Following the consultation session, the consultant emailed the note document to the clinicians.

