During the group consultation session, the consultant asked the clinician to provide any relevant background information about the family or session prior to screensharing the clip. The consultant then screenshared the 5-minute clip and led the group to provide two rounds of feedback. First, the consultant asked each clinician to share positive feedback and/or specific praise about what they observed. Then, the consultant provided her own specific praise about the clip. Next, the consultant directed each clinician to give 1-2 suggestions of constructive feedback about the video clip. The consultant then provided her own constructive feedback comments. After both rounds of feedback were completed, the consultant asked the next clinician to introduce their video clip. She repeated this procedure until all video clips were shown.

Follow-up phase. After the consultation phase, clinicians spent 8 weeks in a follow-up phase in which they were asked to continue delivering Project ImPACT weekly with their client(s). Clinicians did not submit recordings of Project ImPACT telehealth sessions during this period, but were asked to submit one final recorded session and one final questionnaire at the end of the follow-up period. We received 7 sessions in the follow up period; 3 sessions happened to be Session 23: Update Your Child's Goals, which was atypical because it was a goal-setting

session and could not be used for parent coaching fidelity. We decided not to include the 4 remaining follow-up in analyses because there were so few of them.

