Statistical Analysis. An overview the statistical analysis used for each aim is presented in this section. Recent advances in statistical modeling have resulted in the specification of multilevel models that can provide effect sizes for each treatment element while also accounting for the specific features of single-case experimental designs (e.g., handling auto-correlation among consecutive datapoints, correcting for design-specific error structures). These advances have resulted in statistical packages in the R statistics platform (e.g., *sdhlm*). These tools were used to analyze results for Aims 1, 3, and 4. Specific model parameters are presented in the Results section.

Multilevel modeling for Aim 1: Effects of the group consultation model and each consultation component on clinician manual adherence and parent coaching competency. Only data from the 3 agencies with sufficient baseline data were used for Aim 1 analysis. We examined the effects of individual components of the group consultation model (i.e., consultation training activities) on clinician fidelity (i.e., manual adherence, parent coaching competency). To do so, we utilized 2-level multilevel models to estimate the change in level from the average baseline fidelity score to the average fidelity level for each consultation training activity condition (i.e., changes in level from baseline to each consultation condition). For example, the model estimated the magnitude of change from the Baseline level to the Feedback level, and whether the change was statistically significant. Specific model parameters for all models are presented in the Results section.

The models provide two sets of estimates: 1) the average effect of each consultation component on fidelity scores *averaged across clinicians* (i.e., results from the 2-level model),

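### As described, the Aim 1 model tests each component against baseline rather than Feedback against the other two, and has no time or carry-over term

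*Combined protocol and SAP*

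**What the plan says.** Specific Aim 1 predicts that "the feedback component will improve adherence and competence over and above improvements from the case support and skill rehearsal components". Experimental Design and Procedure says that the chosen design "allows for causal interpretation of the effects of treatment elements within a treatment package".

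Multilevel modeling for Aim 1 describes a two-level model for "changes in level from baseline to each consultation condition". Its worked example is the size and significance of the Baseline-to-Feedback change. The fixed effects are one per component. The random effects are a clinician intercept and one effect per consultation phase. Only three agencies enter, and the specific parameters are left to a Results section.

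On the sequence of events:
- From baseline on, clinicians deliver the programme: "they were asked to follow the Project ImPACT coaching manual and meet weekly with their enrolled families" (Design overview).
- Order is randomised by agency, "with each training activity delivered in isolation for a given 4-week consultation period" (Consultation phase). No washout is described. Visual Analysis for Aim 1 explains that repeated baseline and component phases within an agency were not feasible.
- Case Support leaves written material behind: "Following the consultation session, the consultant emailed the note document to the clinicians" (Case support condition).
- Of the follow-up recordings, the plan says "We decided not to include the 4 remaining follow-up in analyses because there were so few of them" (Follow-up phase).

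**The concern.** The prediction compares components with one another; the described tests compare each component with baseline. A significant Baseline-to-Feedback change can occur when Feedback is no better than the others. One component being significant and another not is also no evidence that they differ. Aim 2, by contrast, does compare the components directly, by repeated-measures ANOVA.

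The second gap is conditional. With a single shared baseline and back-to-back blocks, the level in a later block contains that component's own effect, any drift since baseline, and any lasting gain from earlier blocks. Without a term for drift or carry-over, the component effect takes in all three. What is at stake is the purpose of Aim 1: saying which component is the active ingredient.

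**Working it through.** **The plan's own count.** One adherence score plus four PEACE subscales gives 5 outcomes. The plan's 60 separate models / 5 = 12 clinicians, within the 3 × 3 = 9 to 3 × 5 = 15 implied by three agencies of 3-5. Cancellations: 76/299 = 25.4%. No effect size, SD or power is stated for Aim 1.

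**Step 1: test against prediction.** Let bC, bS and bF be the changes from baseline for Case Support, Skill Rehearsal and Feedback. The described tests are of each b against 0. The prediction concerns bF − (bC + bS)/2.

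Illustration (2,000 runs, paired t-tests on clinician phase means as a simplified stand-in for the multilevel model). Assumptions: 12 clinicians, 3 usable baseline sessions, session SD 1, an added component-level SD of 0.3, 25.4% of consultation sessions cancelled, all three components worth 0.5 SD, no drift or carry-over.
- Feedback significant and at least one other not: 27%.
- Feedback alone significant: 10%.
- Direct contrast rejects: 4.3%.

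**Step 2: drift of d per week, no component effect.** With B usable baseline weeks and a block in position k + 1 (k = 0, 1, 2), the gap between midpoints is B/2 + 2 + 4k weeks.

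The three agencies appear to be 2, 5 and 6 (Methodological challenge with the baseline phase). If sessions 1-2 use up two weeks, B is 3-4 for Agency 2 (5-6 minus 2) and 5-8 for Agencies 5 and 6 (6-9, plus 1, minus 2).
- Third-block gap: 1.5 + 2 + 8 = 11.5 weeks (B = 3) to 4 + 2 + 8 = 14 weeks (B = 8).
- Average over positions at mean B = (3.5 + 6.5 + 6.5)/3 = 5.5: 2.75 + 2 + 4 = 8.75d. A generalised least squares projection over all 32 baseline sets × 216 order sets = 6,912 designs gives 8.9d (4.2d to 13.5d).
- Three equal 6-week baselines would give 3 + 2 + 4 = 9.0d, so the stagger alone does not remove the shift.

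For Feedback against the others, let S be the sum of Feedback's positions over three equal-sized agencies (3 to 9). The shift is 4 × [S/3 − (6 − S/3)/2] × d = 2(S − 6)d, from −6d to +6d. It is zero in 56 of 216 order sets; its mean absolute size is 480/216 = 2.2d.

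Rejection rates from the projection (residual SD 1, intercept SD 1, component SD 0.5, 4 clinicians per agency, t with 11 df):

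| Drift (residual SD per week) | 0.02 | 0.04 | 0.08 |
|---|---|---|---|
| Feedback vs baseline | 10% | 24% | 66% |
| Same, AR(1) 0.4 modelled | 8% | 16% | 46% |
| Feedback vs mean of others | 5% | 7% | 12% |
| Same, AR(1) 0.4 modelled | 5% | 6% | 10% |

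**Step 3: a gain G that lasts.**
- Only Case Support works: Feedback vs baseline equals G times the share of agencies where Case Support came earlier, so 0, G/3, 2G/3 or G in 27, 81, 81 and 27 of 216 order sets. Feedback vs others averages −0.25G (−1.0G to +0.5G), against a true −0.5G.
- All three work equally: each baseline contrast is 1G, 2G or 3G by position. Feedback vs others is 0.5(S − 6)G, from −1.5G to +1.5G, although the true value is 0. With G = 1 residual SD the contrast is positive and significant in 23%.

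The direct contrast is thus much less exposed to drift, but it also depends on order under carry-over.

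**The case against.** **The Results section may contain the missing terms.** This stands as a limit. A reader might infer that the fitted model had no contrast and no time term; the documents show only that none is described. The contrast is also a linear combination of the fixed effects already described, so the first gap lies in what is stated and tested, not in the model's structure.

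**The visual analysis already guards against carry-over.** This stands in part. It judges the change in level between adjacent conditions, requires replication in all three agencies, and allows any functional relation in the study to be confirmed only tentatively. If only Case Support works and lasts, the expected change on entering Feedback is zero in every order; if all three work equally and last, each adjacent change is G. But the rule does not remove drift, is order-dependent if gains fade, and does not test Feedback against both other components.

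**Randomised order, staggered baselines and autocorrelation handling.** With three agencies, only 12 of 216 order sets balance every component over positions, and even those leave drift in the baseline contrasts. The stagger separates time from phase only if time is modelled. Autocorrelation handling concerns the errors, not the mean.

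**Drift and carry-over are not shown.** This stands. A reader might take the raised scores in sessions 1-2 as evidence of drift. They concern adherence, are put down to the content of those sessions, and were treated as unusable. Emailed notes show access, not a retained gain. The reason given for playing down trend, however, covers only change within a 4-week period, not change across the study.

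**The rejection rates are not rates of wrong attribution.** A reader might take the 24% at drift 0.04, or the 43% for Feedback vs baseline when only Case Support works and lasts, in that way. Rejecting Feedback vs baseline is not a claim that Feedback beats the others. In a sampled run of the same projection (400 designs, 300 draws each), Feedback was the only significant component in 9.3% and 1.0% of draws. The direct contrast was positive and significant in 3.3% and 1.8%.

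**Conclusion.** The mismatch holds on the text: Aim 1 predicts a difference between components, and the described model tests only differences from baseline. This needs no assumption about drift or carry-over, and it should be fixed.

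The second part is conditional. With no drift and no carry-over the bias is zero. Otherwise the baseline contrasts are cumulative and order-dependent, by about 8.9 weeks of drift on average, or by up to 3G for a component placed third when all gains are equal and last.

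The sizes rest on assumed SDs and drifts, about one session per week, equal agency sizes, and complete consultation in all three agencies. One of the six agencies stopped after 6 of 12 sessions, and the documents do not say whether it is among the three. The realised orders in Table 2 are not in the text available here, so the actual imbalance cannot be computed.

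The documents do not support the stronger conclusion that the reported component effects are biased or that Feedback's effect is spurious.

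**What to change.** The document is retrospective, so label every addition post hoc. Keep the stated model, and:

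1. For each of the 5 outcomes, report Feedback minus the mean of the other two components, with its confidence interval, as the test of the Specific Aim 1 prediction, beside the realised Table 2 orders.
2. As sensitivity analyses, report the same contrast from one fit with weeks since the start of baseline and one in which each component's indicator stays on after its block.
3. State that baseline-to-component estimates may include drift or retained effects of earlier components, and that under carry-over the contrast itself depends on order.
4. If the contrast changes materially across fits, describe attribution to Feedback as uncertain.

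Do not require significance in all three fits. In the projection, a true lasting Feedback-only gain of 1 SD would pass that rule in only 31% of cases, and in 1% if Feedback came first in all three agencies.

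**Cost:** one contrast per outcome, 2 × 5 = 10 extra fits, a few sentences, and wider intervals with 12 clinicians. At component SD 0.5:
- The weeks term raises the SE of Feedback vs baseline by a median of 1.5 times (1.3-3.3) and of Feedback vs others by 1.03 times (1.0-1.8). It can absorb a true lasting effect: a permanent Feedback gain of 10 is estimated against baseline at 6.0 on average (2.2-10).
- The stay-on coding makes the SE of Feedback vs others 1.3-1.5 times larger on average. If a Feedback gain of 10 lasts only during its block, this coding gives 12.5 (10-15) for that contrast.

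Neither fit is a reference standard; they show how far the answer depends on the assumption.
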